10.1 Study Design

This study is a prospective, open-label, single-centered, phase II trial.

10.2 Sample Size and Accrual and Data Analyses Plans

Tumor Registry data at UCIMC shows that we have had 960 patients with Hormone Receptor positive breast cancer from 2012-2017. The 2018 data is currently not populated by the tumor registry. Similarly, from 1/1/14 to 6/14/2019, there have been 456 patients accrued in breast cancer trials out of which, 155 patients were enrolled in treatment trials. In order to obtain 30 evaluable breast cancer participants to examine the primary hypothesis, we will need to screen 680 invasive breast cancer patients (this is clearly possible due to the cohort of 960 patients from 2012-2017). Based on the data from California Cancer Registry and estimated percentage of recurrence, we estimate that approximately around 10% of 680 invasive breast cancer patients are post-menopausal, have histologically been confirmed with HR+, have localized non-metastatic breast cancer and will have recurrence. Of the 68 patients, we estimate that there are 59 (87% of 68) patients who are also on adjuvant endocrine therapy. The mutation ESR1 is

CONFIDENTIAL

This material is the property of the [UC Irvine Chao Family Comprehensive Cancer Center](#). Do not disclose or use except as authorized in writing by the study sponsor.

detected in 11-54% of patients with advanced breast cancer especially during the progression of hormonal therapy. Therefore, we estimate that there are 32 (54% of 59) patients who have ESR1 gene mutation/any known molecular evidence of endocrine resistance. To take into account of 5% attribution, we will need to enroll 32 subjects to receive the study treatment to ensure that there are 30 evaluable breast cancer participants. The plan of enrollment is over a four-year period. Hence, with the adequate number of patients justified from UCIMC tumor registry data and extending the period of enrollment from to four years, enrolling the sample size of 30 patients over a period of four years is feasible.

Table x1:Power and sample sizes of Simon's two-stage design

N	n ₁	r ₁	r ₂	Type 1 Error	Power	EN ₀	Probability of early stopping	p ₀	p ₁
29	10	1	5	0.0471	0.8051	15	0.7361	0.1	0.3

Table X1 presents sample size of Simon's two-stage design. Where n is the total number of subjects, n₁ is the number of subjects accrued during stage 1, if r₁ or fewer responses are observed during stage 1, the trial is stopped early for futility. If r₂ or fewer responses are observed by the end of stage two, then no further investigation of the drug is warranted, EN₀ is the expected sample size for the trial when response rate is p₀ and p₀ and p₁ are the response probabilities under the null and under the alternative hypothesis. Thus, the null hypothesis that the true response rate is 10% will be tested against a one-sided alternative. In the first stage, 10 patients will be accrued. If there are one or fewer responses in these 10 patients, the study will be stopped. Otherwise, 19 additional patients will be accrued for 29. The null hypothesis will be rejected if 6 or more responses are observed in 29 patients. This design will yield a type I error rate of 0.0471 and power of 80% when the true response rate is 0.3. Thus, we anticipate recruiting 29 evaluable participants with at least 10 in stage 1. (Simon 1984, Jung et al 2004) (16, 17). Given the sample size of 30 participants, power in the statistical design will be low for the secondary and exploratory endpoints. Efficacy of the study as measured by estimating the objective response rate in the breast and/or the axillary lymph nodes or determining if the combination of Abemaciclib and Fulvestrant increases the percentage of patients who undergo breast conserving surgery will be measured by constructing 95% CI. We plan to use survival analysis methods such as Kaplan- Meier estimates of survival probability for univariate analysis and log rank tests in order to test for differences among different patient characteristics such as age group for recurrence or disease-free survival. For multivariate analysis in order to examine survival adjusted for a number of covariates we plan to use the Cox proportional hazards model. In order to examine the safety and toxicity which will be determined by the incidence of treatment-emergent, treatment-related adverse events (TRAEs), and serious adverse events (SAE) we plan to monitor side effects and adherence to the protocol throughout the duration of the study. Interim analyses will be performed to assess the presence of side effects. Contingency tables will be constructed to compare the proportion of patients with side effects by study characteristics as age, race ethnicity and other clinical and epidemiologic characteristics. Distributions of all data items will be generated and examined for the presence of outliers, in order to assess the general form of the distributions, and to compute measures of central tendency and variability. Trellis graphics will be used for data display including histograms, boxplots, and Q-Q normal plots. In addition, we plan to examine if genomic analysis of patient matched breast tissue samples and serial mutational tracking of circulating tumor DNA can identify new mechanisms of endocrine resistance and how

CONFIDENTIAL

This material is the property of the UC Irvine Chao Family Comprehensive Cancer Center. Do not disclose or use except as authorized in writing by the study sponsor.

Abemaciclib overcomes endocrine resistance. For the analyses with matched pair tissue data we will use paired t tests or Wilcoxon sign rank statistical analysis in order to test differences in recurrent and treated breast tissue. We plan to measure absolute values and changes in circulating tumor DNA and correlate them with endocrine resistance. If serial monitoring of ctDNA can provide markers of resistance, we will quantify endocrine resistance as a composite outcome that will be quantified as dichotomous variable if it happens (yes or no) and at what time interval during our study. We will start our analysis by using frequency table analysis in order to examine the relationship between resistance or sensitivity and specific mutations.

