2.4 Endpoints

The primary endpoint is pathological complete response (pCR) as defined by no evidence of tumor cells in the final surgical specimen
The secondary endpoints are ORR per RECIST 1.1 criteria, recurrence disease-free and incidence of AEs

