4.8 Patient Replacement

Patients will not be replaced

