6.2.1 Definitions

Evaluable for toxicity. All patients will be evaluable for toxicity from the time of their first treatment with study drug.

Evaluable for objective response. Only those patients who have measurable disease present at baseline, have received at least one cycle of therapy, and have had their disease re-evaluated will be considered evaluable for response. These patients will have their response classified according to the definitions stated below. (Note: Patients who exhibit objective disease progression prior to the end of cycle 1 will also be considered evaluable.)

CONFIDENTIAL

This material is the property of the [UC Irvine Chao Family Comprehensive Cancer Center](#). Do not disclose or use except as authorized in writing by the study sponsor.

Evaluable Non-Target Disease Response. Patients who have lesions present at baseline that are evaluable but do not meet the definitions of measurable disease, have received at least one cycle of therapy, and have had their disease re-evaluated will be considered evaluable for non-target disease. The response assessment is based on the presence, absence, or unequivocal progression of the lesions.

6.2.2 **Disease Parameters**

Measurable disease. Measurable lesions are defined as those that can be accurately measured in at least one dimension (longest diameter to be recorded) as ≥ 20 mm with conventional techniques (CT, MRI, x-ray) or as ≥ 10 mm with spiral CT scan. All tumor measurements must be recorded in millimeters (or decimal fractions of centimeters).

Note: Previously irradiated lesions are non-measurable except in cases of documented progression of the lesion since the completion of radiation therapy.

Non-measurable disease. All other lesions (or sites of disease), including small lesions (longest diameter <20 mm with conventional techniques or <10 mm using spiral CT scan), are considered non-measurable disease. Bone lesions, leptomeningeal disease, ascites, pleural/pericardial effusions, lymphangitis cutis/pulmonis, inflammatory breast disease, abdominal masses (not followed by CT or MRI), and cystic lesions are all non-measurable.

Note: Cystic lesions that meet the criteria for radiographically defined simple cysts should not be considered as malignant lesions (neither measurable nor non-measurable) since they are, by definition, simple cysts.

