10.0 STATISTICAL CONSIDERATIONS

Pathological response (pCR) is a tool to measure the efficacy of Neo-Adjuvant therapy. A complete pCR is defined as the absence of invasive cancer in the tumor and/or the axillary lymph node in the surgical pathology specimen after undergoing Neo-Adjuvant therapy. Chemotherapy can shrink HR- positive tumors and facilitate better surgical options, but is less likely to achieve a pathologic complete response (pCR) in HR-positive cancers, especially luminal A cancers, than for more proliferative histologies. Multiple metaanalysis have shown that pCR has prognostic implications even in patients with HR+ breast cancer. However, a limitation of using pCR to predict outcomes in patients with ER+ disease is that only 2 to 10 percent of patients with ER + disease achieve a pCR with NACT. In the post-menopausal setting, Aromatase Inhibitors are recommended over Tamoxifen as Neoadjuvant endocrine therapy based on clinical trials and meta-analysis. AIs resulted in higher clinical response rate (OR 1.69, 95% CI 1.36-2.10), radiologic response rate (OR 1.49, 95% CI 1.18-1.89), and BCS rate (OR 1.62, 95% CI 1.24-2.12) compared with tamoxifen (18).

Several trials have also investigated the role of endocrine therapy in combination with other targeted therapies. For example, in the randomized phase II UNICANCER-NEOPAL study, the combination of neoadjuvant palbociclib and letrozole resulted in slightly lower pCR rates compared with neoadjuvant third-generation chemotherapy, but the rates of clinical response and breast-conserving surgery were similar, with less frequent serious adverse events (19). Another study compared different doses of neoadjuvant fulvestrant (500 mg/month versus 250 mg/month) given for 16 weeks prior to surgery (20). Similar to what has been observed in the metastatic setting, the study demonstrated that the higher dose of fulvestrant was superior and had a greater antiproliferative effect. At week 16, tumor response rates were 22.9 and 20.6% for fulvestrant 500 and 250 mg, respectively, with considerable decline in all markers by both imaging and the ER/PR scoring method.

CONFIDENTIAL

This material is the property of the [UC Irvine Chao Family Comprehensive Cancer Center](#). Do not disclose or use except as authorized in writing by the study sponsor.

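### Section 10.2 tests pCR at 29 patients but plans 30 evaluable from 32 treated, and never defines evaluable for pCR or says how patients without a specimen, or beyond 29, are counted

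*Combined protocol and SAP*

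**What the plan says.** The primary endpoint in section 2.4 is "pathological complete response (pCR) as defined by no evidence of tumor cells in the final surgical specimen". Section 6.1 likewise reads pCR in the surgical specimen, so a patient without one has no observed outcome.

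Section 10.2 gives two counts for the primary hypothesis. The accrual paragraph allows 5% for losses (printed as attribution, evidently attrition) and concludes that "we will need to enroll 32 subjects to receive the study treatment to ensure that there are 30 evaluable breast cancer participants". The design paragraph and Table x1 use N = 29, with 10 patients in stage 1: "Otherwise, 19 additional patients will be accrued for 29", and "The null hypothesis will be rejected if 6 or more responses are observed in 29 patients". It then sums up: "Thus, we anticipate recruiting 29 evaluable participants with at least 10 in stage 1". A later sentence in the same section returns to a sample size of 30, as does the study summary.

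Evaluability is defined in section 6.2.1 for toxicity, objective response and non-target disease. The objective-response definition begins "Only those patients who have measurable disease present at baseline, have received at least one cycle of therapy" and then asks for re-evaluation of disease. It mentions no surgical specimen, and nothing equivalent is written for pCR. Section 4.8 states "Patients will not be replaced". Sections 4.5 and 5.6 list ways in which treatment or participation can end early, including progression, death, toxicity and withdrawal.

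**The concern.** Two things that fix the primary denominator are missing.

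First, the plan does not say how a treated patient without a specimen is counted, at stage 1 or at the end. The 5% allowance is attached to subjects who receive treatment, and the target is a number of evaluable participants, so the natural reading is that such patients leave the denominator. Those who never reach surgery, for example because of death, withdrawal or disease no longer operable, are unlikely to be a random subset. Leaving them out makes the pCR rate look better than it was among all patients treated.

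Second, if losses run as planned there will be about 30 evaluable patients, and up to 32 treated, for a rule calibrated at 29. Nothing says whether patients 30 to 32 enter the test, the estimate, both or neither.

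The trial is open-label and single-arm, and it decides on small counts. An unwritten denominator could be settled after the pathology results are known.

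**Working it through.** **Inputs.** From section 10.2: n1 = 10, stop at 1 or fewer; N = 29, reject at 6 or more; p0 = 0.10, p1 = 0.30; 5% loss; 32 treated, 30 evaluable. From section 4.8: no replacement. Assumptions not in the documents are marked as such.

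**1. The plan's own figures.** With X1 ~ Bin(10, p) and Y ~ Bin(N − 10, p),

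P(reject) = Σ (x = 2 to 10) P(X1 = x) · P(Y ≥ 6 − x).

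- N = 29, p = 0.10: 0.0471 (stated 0.0471).
- N = 29, p = 0.30: 0.8051 (stated 0.8051).
- Early stopping under p0: 0.9^10 + 10 · 0.1 · 0.9^9 = 0.7361 (stated 0.7361).
- Expected sample size under p0: 10 + 0.2639 · 19 = 15.0 (stated 15).

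Table x1 is correct for 29 patients.

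**2. The accrual count.** 30/0.95 = 31.6, rounded up to 32, and 32 · 0.95 = 30.4. This is also correct, but for a target of 30. For 29 it would be 29/0.95 = 30.5, or 31.

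**3. The cut-off of 6 applied to the planned counts.** Same formula, stage 1 unchanged, p = 0.10:

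| N analysed | Type I error |
|---|---|
| 29 | 0.0471 |
| 30 | 0.0525 |
| 32 | 0.0640 |

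Moving the cut-off to 7 is not a free repair: at N = 30 it gives type I error 0.0206 and power 0.7587.

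**4. Effect on the reported rate.** With 6 responses, 30 evaluable and 32 treated: 6/30 = 20.0%, 6/32 = 18.8%.

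**5. Effect of exclusion on the test.** Assume that p0 = 10% is an all-treated rate and that no excluded patient had pCR. With a fraction f excluded, the null rate among those analysed is 0.10/(1 − f); at f = 0.05 this is 0.1053. The number evaluable is E ~ Bin(T, 1 − f) for T treated, and the first min(E, 29) are analysed with the cut-off of 6.

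| Case | Type I error |
|---|---|
| f = 5%, 29 evaluable always reached | 0.0578 |
| f = 5%, T = 32 | 0.0571 |
| f = 2/32 = 6.25%, T = 32 | 0.0596 |
| f = 5%, T = 29 (no later patients to fill in) | 0.0490 |
| f = 5%, T = 32, excluded patients have 5% pCR (assumed) | 0.0517 |
| f = 5%, T = 32, all-treated null 9.5% (assumed) | 0.0466 |

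Of the rise from 0.0471 to 0.0571, only 0.0490 − 0.0471 = 0.0019 remains when 29 are treated. The rest comes from patients 30 to 32 taking the vacated places. If p0 is an operated-patient rate, those analysed have a 10% rate and there is no inflation.

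**6. Cost of counting a missing specimen as no pCR, first 29 dosed.** If 10% and 30% were meant per operated patient, the all-treated rates are p(1 − f).

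- f = 5%: power 0.7655, type I error 0.0382.
- f = 2/32: power 0.7547.
- For comparison, excluding such patients with 32 treated keeps power at 0.8038 (5%) and 0.8025 (2/32).
- If 30% is the all-treated target, power stays at 0.8051.

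**The case against.** The sponsor can answer that the test is printed consistently at 29 in Table x1, in the 10 + 19 split, in the rejection rule and in the evaluable count that closes the design description. On that view 32 is a correctly computed recruitment cushion, one patient above the minimum, and the bar on replacement is what one would write after building in such a cushion. This stands: neither Table x1 nor the step from 30 to 32 contains an error, and no sentence says that the cut-off of 6 applies to 30 or 32 patients. The figures 0.0525 and 0.0640 show what happens if the silence is filled that way.

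A reader might infer that the text is evenly balanced between dropping patients without a specimen and counting them as failures. It is not. Speaking of patients accrued is ordinary two-stage language, and section 4.8 does not imply that losses are non-responses. The text leans towards an evaluable denominator, though the 5% could also cover losses before dosing.

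A reader might also infer that exclusion breaks the type I error. The documents do not support this. The inflation needs p0 to be an all-treated rate, the true rate to be exactly 10%, and no pCR among those excluded. The plan does not say which population p0 describes. The only historical range it gives is that "only 2 to 10 percent of patients with ER + disease achieve a pCR with NACT", so 10% is already the top of that range. The rejection rule is also a count of responses: dropping a non-responder adds none, unless a later patient takes the place.

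Finally, few patients should be affected, since the study summary sends patients on to surgery after the treatment phase. That limits the size of the problem but does not supply the missing rule.

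**Conclusion.** The point holds as a gap in the primary analysis that should be fixed, of modest size. Evaluable is undefined for pCR, the wording favours a denominator that flatters the reported rate (20.0% against 18.8% at the boundary), and patients 30 to 32 have no assigned role although the plan expects to treat them. If they enter the test under the printed cut-off, the stated 0.0471 becomes 0.0525 or 0.0640; this does not depend on how missing specimens are handled.

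The effect of exclusion on the test is secondary and conditional: about 0.057 at the plan's own 5% loss under the assumptions in step 5, mostly because later patients fill the 29, and none if p0 refers to operated patients. It would be wrong to conclude that the design's error rates are miscalculated or that the trial as planned has a demonstrably inflated type I error.

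**What to change.** State the following in section 10.2.

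- The primary test uses the first 29 patients who received at least one dose, in enrolment order; the first 10 form stage 1.
- Any of these without an evaluable surgical specimen, whether through no definitive surgery or no readable pathology, counts as not achieving pCR at both stages.
- Patients dosed beyond the 29th enter the reported pCR estimate and its confidence interval under the same rule, but not the test.
- The pCR rate among patients with a specimen is reported as a sensitivity analysis.
- p0 = 10% and p1 = 30% are all-treated rates.

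This takes a few sentences and no new data. There are two costs. The patients above 29 no longer make up for losses in the test and serve only the estimate, so test and estimate can have different denominators. If 30% was meant per operated patient, power falls from 0.805 to 0.766 at 5% not operated (0.755 for 2 of 32) and type I error becomes conservative (0.038 at 5%); the stated power should then be restated. If 30% is the all-treated target, the stated error rates stand.

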4.6 Duration of Follow Up

Patients will be followed every 6 months after surgery for ctDNA blood collection. The follow up phase will continue until study completion at 5 years or until death, whichever occurs first.

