6.2.7 Recurrence Disease Free Survival

Recurrence disease free survival will be defined as the time from surgery until patient develops recurrence.

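### A Cox model with an unlimited number of covariates is planned for recurrence in about 29–32 patients, where an assumed 2–16 events cannot support several covariates

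*Combined protocol and SAP*

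**What the plan says.** Section 10.2 plans Kaplan-Meier estimates, "log rank tests in order to test for differences among different patient characteristics such as age group for recurrence or disease-free survival", and then a regression: "For multivariate analysis in order to examine survival adjusted for a number of covariates we plan to use the Cox proportional hazards model". The Statistical Methodology row of the Study Summary repeats the same three analyses.

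The features that determine how many events this model will have are spread across the protocol:

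- Endpoint (Section 6.2.7): "Recurrence disease free survival will be defined as the time from surgery until patient develops recurrence". Patients who never reach surgery contribute nothing, and deaths are not mentioned.
- Sample size (Section 10.2): stage 1 has 10 patients, with the futility rule "If there are one or fewer responses in these 10 patients, the study will be stopped". For a trial that passes this look, the plan reads: "Otherwise, 19 additional patients will be accrued for 29". The same section plans to enrol 32 so as to have 30 evaluable, and the Study Summary gives 30.
- Accrual (Section 10.2): "The plan of enrollment is over a four-year period".
- End of follow-up (Section 4.6): "The follow up phase will continue until study completion at 5 years" or death. The Study Summary gives a study duration of 5 years.
- Start of the clock: surgery follows treatment to maximum response as judged by the investigator (Section 4.5), so the delay from entry to surgery is not fixed.

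Section 10.2 concedes low power for secondary and exploratory endpoints. No recurrence rate or expected event count appears anywhere.

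**The concern.** The information in a Cox model comes from events, not patients. Here a small cohort enters over most of the study's life, and its recurrence clock starts only at surgery, so events will be few. With several covariates and few events, some combination of covariates may separate the patients who recur from those who do not. An estimate then runs to infinity. If the model does converge, its hazard ratios can be far from the truth by chance alone.

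Because the covariates are neither named nor limited, the choice of model is also left open until the data are in hand. The output would be a table of adjusted hazard ratios that looks like a planned result but carries little information. The primary pCR test and the stopping rule do not depend on it.

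**Working it through.** **1. The plan's own figures.** The documents give no figure for the Cox analysis, so the design figures are checked first. With 10 patients and a 10% response rate, P(at most 1 response) = 0.9^10 + 10 × 0.1 × 0.9^9 = 0.3487 + 0.3874 = 0.7361. The expected sample size is 10 + 19 × (1 − 0.7361) = 15.0. The exact two-stage sums give a type I error of 0.0471 and power of 0.8051. Enrolment is 30/0.95 = 31.6, rounded up to 32. All agree with Section 10.2.

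**2. Expected recurrences.**

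Inputs from the documents: n = 29 or 32, accrual over 4 years, end at 5 years, time counted from surgery.

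Assumptions: uniform accrual, constant recurrence hazard h, surgery s = 0.5 or 1.0 year after entry, every patient operated on.

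Post-surgery follow-up is then uniform from 1 − s to 5 − s years, with mean 2.5 years (s = 0.5) or 2.0 years (s = 1.0), and

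E(events) = n × {1 − [exp(−h(1 − s)) − exp(−h(5 − s))] / (4h)}.

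Example: h = 0.30, s = 0.5, n = 32 gives 32 × {1 − (0.8607 − 0.2592)/1.2} = 32 × 0.4988 = 16.0.

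| Hazard per year | n = 29, s = 0.5 / 1.0 | n = 32, s = 0.5 / 1.0 |
|---|---|---|
| 3% | 2.1 / 1.7 | 2.3 / 1.9 |
| 10% | 6.3 / 5.1 | 6.9 / 5.6 |
| 20% | 10.9 / 9.0 | 12.1 / 10.0 |
| 30% | 14.5 / 12.1 | 16.0 / 13.4 |

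The range is about 2 to 16.

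If stage 1 stops the trial at 10 patients, the same formula gives 0.6 to 5.0. Even with 5 years of follow-up from surgery for all 10, annual recurrence probabilities of 3–30% give 10 × (1 − 0.97^5) = 1.4 to 10 × (1 − 0.70^5) = 8.3.

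**3. Precision with one balanced binary covariate.** SE(log HR) = √(4/d) for d events, so the 95% interval extends by a factor exp(1.96 × √(4/d)) either side of the estimate. That factor is 16 at 2 events, 5.8 at 5, 3.3 at 11 and 2.8 at 15. Power to detect a hazard ratio of 2 (two-sided 5%) is 7% at 2 events and 21% at 11. It is 46% even if all 29 patients recur.

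**4. Can the model be fitted?** Ordinary Cox fits were simulated with n = 29, surgery at 6 months and balanced binary covariates with no effect, 1,500 trials per setting. A fit was counted as failed if it did not converge or a standard error exceeded 5.

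| Mean events | Failed: 1 covariate | 3 covariates | 5 covariates | Median upper/lower CI ratio: 3 / 5 covariates |
|---|---|---|---|---|
| about 2 | 57% | 77% | 87% | 129 / 172 |
| 3.4 | 31% | 53% | 66% | 87 / 125 |
| about 6.5 | 6% | 16% | 24% | 31 / 43 |
| 12 | 0.5% | 1% | 1.4% | 13 / 16 |
| 16 | 0.1% | 0.1% | 0.3% | 9 / 11 |

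The interval ratios are from the fits that succeeded.

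With a true hazard ratio of 2 for one of three covariates, failures were 58% at about 3.5 events, 18% at 6.5 and 2% at 11. Among the fits that survived, 16–23% gave a hazard ratio above 4 or below 1/4.

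**The case against.** The plan already says that power will be low for secondary endpoints, and this is one sentence about one of them. At 10 or more events a three-covariate model nearly always converges, so calling it inestimable across the board would be wrong. The recurrence hazards are assumed. Section 1.4 describes a high-risk group, so rates could sit at the upper end, and counting deaths would add events. If follow-up were read as 5 years from surgery for each patient, 29 patients would give 29 × (1 − 0.97^5) = 4.1 to 29 × (1 − 0.70^5) = 24.1 recurrences at 3–30% per year.

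Much of this stands. Failure to fit is mainly a problem below about 5 events, and above that the fault is imprecision. It does not rescue the plan. A low-power caveat warns of missed effects. It does not limit the number of covariates, warn that the model may not converge, or say what to do if it does not. With 16 events and three covariates the upper confidence limit is still typically 9 times the lower.

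Three stronger readings are tempting and are not supported:

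- **Systematic bias away from the null.** With a true log hazard ratio of 0.69 and three covariates, surviving fits had mean 0.77 and median 0.73 at about 11 events, and median 0.72 at about 6. At about 3 events they were not consistently inflated.
- **A ceiling of 29 patients.** That is the evaluable number for the pCR test. Section 10.2 enrols 32, and Section 6.2.7 does not restrict recurrence analyses to the evaluable set.
- **A fault in the log-rank tests.** Nothing here shows one, so there is no case for removing their p-values.

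**Conclusion.** The concern holds as a minor point about the analysis plan. An ordinary Cox model with an open number of covariates does not suit about 29–32 patients, still less the 10 who would remain after a stage 1 stop, which has probability 0.74 if the true response rate is 10%. With several covariates the model often cannot be estimated below about 5 events. At 6–12 events it usually fits, but very imprecisely and with frequent extreme hazard ratios.

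The 2–16 event range rests on assumed hazards of 3–30% per year, uniform accrual and surgery at 6–12 months; none of these is in the documents. The conclusion is less sensitive than the range: at no event count examined does a model with several covariates give usefully precise adjusted hazard ratios.

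**What to change.** In Section 10.2 and the Statistical Methodology row of the Study Summary, replace the multivariable Cox analysis with descriptive Kaplan-Meier estimates of recurrence-free probability and confidence intervals at fixed, pre-stated times after surgery.

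If a Cox model is kept, it should:

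- take at most one covariate at a time, each named in advance;
- use a Firth penalty, so that estimates stay finite under separation;
- be run only above a stated minimum number of events;
- be labelled exploratory.

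The threshold is for the sponsor to set. Ordinary one-covariate fits failed in 31% of simulated trials at 3.4 events, 6% at about 6.5 and 0.5% at 12, so something near ten would be defensible.

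This changes wording only, with no effect on patients, data collection or the primary analysis. The cost is that no multivariable-adjusted hazard ratios are reported. The penalty does not add information, so single-covariate intervals will remain wide.
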